#### Number of Participants:

Up to a total number of 16 participants will be enrolled in Cohorts 1 and 2. A total of 30 participants will be enrolled in Cohort 3.

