# 9. STATISTICAL METHODS

In general, summary statistics (n, mean, standard deviation, median, minimum and maximum values for continuous variables, and number and percentage of participants in each category for categorical variables) will be provided by treatment group and cohort for all variables.

Baseline value is defined as the last non-missing assessment prior to the first dose of study drug, except for serum AAT where baseline is defined as the mean from all predose AAT measurements.

Source data for the summary tables will be presented as by-subject data listings.

All statistical tests will be 1-sided with a type I error rate of 5%, unless otherwise specified.

Complete details of the statistical analysis will be outlined in the SAP and finalized before the interim analysis database lock.

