The study will include 3 cohorts. In Cohorts 1 and 2 there will be up to 8 participants in each cohort (randomization scheme ratio of 3:1 active: placebo). The sample size for Cohort 1 and Cohort 2 is based on clinical consideration rather than statistical power calculation.

The primary endpoint for Cohort 3 of this study is the percentage change from baseline in serum and liver Z-AAT protein concentration at week 24. Assuming the percentage change from baseline is 80%, 60% and 10% in the active high dose group, active low dose group and placebo group respectively, and the standard deviation is 0.5 for all three groups, a sample size of 10 participants per treatment group will provide at least 80% power to detect a statistically significant difference between active high dose group and placebo, and between active low dose group and placebo, at an overall 1-sided significance level of 0.05.

The F1/F2, F3, and F4 fibrosis types will be used as randomization stratification factors for all 3 cohorts.

2.3 **Study Endpoints**

2.3.1 *Primary Endpoints*

The primary endpoints for Cohorts 1 and 2 are:

- The incidence and nature of treatment emergent adverse events (TEAEs), and the change from Baseline in pulmonary function tests (PFTs), 12-lead electrocardiograms (ECGs), physical examination (PE) findings, vital signs, and clinical laboratory tests
- Changes from baseline to weeks 24 (Cohort 1)/ 48 (Cohort 2) in serum AAT protein concentrations

The primary endpoints for Cohort 3 are:

- Change from baseline to week 24 in serum AAT protein levels
- Change from baseline to week 24 in liver AAT protein levels

2.3.2 *Secondary Endpoints*

The secondary endpoints are:

- PK profile of belcesiran
- Change from baseline up until week 96 in liver fibrosis
- Change from Baseline up until week 96 in diastase-resistant PAS-positive AAT globules

2.3.3 *Exploratory Efficacy Endpoints*

The exploratory endpoints are:

- Change from Baseline up until week 96 in FibroScan® score
- Change from Baseline up until week 96 in enhanced liver fibrosis (ELF) score
- Change from Baseline up until week 96 in cytokeratin 18 (CK-18)

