3.4 Safety & Efficacy Assessment

3.4.1 Primary Endpoint for Cohorts 1 and 2

Safety Analysis:

All safety analyses will be performed on the Safety Population. The details of the safety analysis are described in section 3.7.

Serum AAT Concentrations Analysis:

Serum AAT protein concentration observed data, absolute change from baseline, and percent change from baseline will be summarized with descriptive statistics by treatment and time point, based on the PD Population.

The data from the date of and onwards of augmentation therapy received will be excluded from the analysis. The augmentation therapy includes Prolastin® and Glassia®.

Correspondingly, figures for observed serum AAT protein concentration longitudinal trajectory, absolute change from baseline, and percent change from baseline will be presented by line plot (mean \pm standard error (SE)) at the individual level and at the cohort level using the linear scale. Figures will include all study periods, relevant references and legends.

The serum AAT concentration will be analyzed by using a linear log-normal regression model by combining Cohort 1 and Cohort 2 together. The linear log-normal regression will include treatment, baseline value and randomized stratification factor for fibrosis types (F1/F2, F3 and F4) as covariate and the change from baseline in serum AAT as the response variable.

The sample SAS code is as follows.

```
/******  
datain=Input data set  
TRT= Treatment (0-Placebo, 1-Belcesiran 210 mg)  
FIB= Fibrosis types (F1/F2, F3, and F4)  
BASE=Baseline serum  
CHG= Serum change in Week 24 from baseline  
*****/  
proc genmod data=datain;  
class TRT FIB;  
model CHG = TRT BASE FIB / dist=normal link=log;  
lsmeans TRT/ PDiff CL alpha=0.05;  
run;
```

The least square mean difference between the Belcesiran 210 mg and Placebo, standard error, and the confidence interval will be reported.

The P-value will not be reported since the hypothesis test will not be performed.

3.4.2 Primary Endpoint for Cohort 3

There are no data for Cohort 3 due to the early termination of the study prior to enrolling participants in this cohort. Therefore, no analysis is planned for Cohort 3.

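### SAP 3.4.1 leaves its only between-arm interval to PROC GENMOD defaults; with 16 participants, a fittable version of the model would cover about 87%, not 95%

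*SAP*

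**What the plan says.** SAP 3.4.1 pools Cohorts 1 and 2 and models the change from baseline in serum AAT on treatment, baseline and fibrosis stratum. The sample code opens with "proc genmod data=datain", specifies "model CHG = TRT BASE FIB / dist=normal link=log" and requests limits with "lsmeans TRT/ PDiff CL alpha=0.05". The fibrosis factor has three levels: "FIB= Fibrosis types (F1/F2, F3, and F4". Neither the code nor the text gives a scale option, a small-sample correction or degrees of freedom.

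On output, SAP 3.4.1 states: "The least square mean difference between the Belcesiran 210 mg and Placebo, standard error, and the confidence interval will be reported". It withholds the p-value, and SAP 3.1.5 drops all hypothesis tests. The other SAP analyses are descriptive, so this is the only between-arm standard error and interval in the plan.

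On numbers, SAP 2.2.4 says: "In Cohorts 1 and 2 there will be up to 8 participants in each cohort". The Protocol synopsis agrees: "Up to a total number of 16 participants will be enrolled in Cohorts 1 and 2". Allocation is 3:1. The analysed number can be smaller, because SAP 3.4.1 removes AAT data from the date augmentation therapy is received and SAP 3.1.6 does not impute missing values.

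**The concern.** For a normal response, GENMOD with no scale option estimates the residual variance by maximum likelihood, dividing the residual sum of squares by n and not by n-p. Its Wald limits use the normal quantile 1.960 and not a t quantile. In a large trial neither choice matters. Here at most 16 observations support five mean parameters, which leaves 11 residual degrees of freedom at best, and both choices shorten the interval.

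Serum AAT change is a primary endpoint for these cohorts. With no test and no p-value, this standard error and interval are the plan's only statement of uncertainty about the treatment difference. A reader will take alpha=0.05 to mean 95% and will credit the estimate with more precision than it has.

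**Working it through.** **Inputs.**
- Nominal level: alpha=0.05 on the LSMEANS statement, a two-sided 95% interval with z = 1.960 (SAP 3.4.1). The Protocol section 9 convention, "All statistical tests will be 1-sided with a type I error rate of 5%, unless otherwise specified", concerns tests, which the SAP no longer performs.
- Maximum n: 2 × 8 = 16 (SAP 2.2.4; Protocol synopsis).
- Mean parameters: intercept 1 + treatment 1 + baseline 1 + fibrosis 2 = 5, if all three strata are occupied (SAP 3.4.1).
- Analysed n below 16: not given in the documents. I assume 12 to 16 and also show 10.
- GENMOD defaults (RSS/n, normal quantiles): software behaviour, not stated in the SAP.

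**Formula.** In a linear normal model with equal variances, the estimate minus its true value, divided by the standard error based on RSS/(n-p), follows t(n-p). The GENMOD standard error is that one multiplied by sqrt((n-p)/n). Hence:

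- Coverage = P(|t(n-p)| ≤ 1.960 × sqrt((n-p)/n))
- Required widening = t(0.975, n-p) / [1.960 × sqrt((n-p)/n)]

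At n=16, p=5: sqrt(11/16) = 0.829, and 1.960 × 0.829 = 1.625. P(|t(11)| ≤ 1.625) = 86.8%. Widening = 2.201/1.625 = 1.35.

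| n | df | SE factor | Coverage | Widening needed |
|---|---|---|---|---|
| 16 | 11 | 0.83 | 86.8% | 1.35 |
| 14 | 9 | 0.80 | 85.0% | 1.44 |
| 12 | 7 | 0.76 | 82.2% | 1.58 |
| 10 | 5 | 0.71 | 77.6% | 1.86 |

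**Which construction returns the nominal 95%?** (p=5)

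| Variance | Quantile | n=16 | n=12 |
|---|---|---|---|
| RSS/n | normal | 86.8% | 82.2% |
| RSS/n | t(n-p) | 90.5% | 88.6% |
| RSS/(n-p) | normal | 92.4% | 90.9% |
| RSS/(n-p) | t(n-p) | 95.0% | 95.0% |

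Only the last row does. SCALE=PEARSON alone gives the third row.

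**Empty fibrosis strata.** With one stratum unobserved (p=4), coverage is 88.5% at n=16 and 85.2% at n=12. With the factor gone altogether (p=3), it is 89.9% and 87.6%.

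**Simulation check** (3:1 arms, assumed baseline and stratum distributions). A linear model with 20,000 runs gave 86.7% at n=16, 85.3% at n=14 and 82.1% at n=12. A normal log-link model with a positive mean response, 4,000 runs for each of three settings, gave 86.8-87.3% at n=16 and 82.5-83.7% at n=12. In one of those settings 8.5% (n=16) and 14.5% (n=12) of fits failed and were left out.

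**The code as written.** A log link forces a positive fitted mean, but the expected change is negative: Protocol 4.3 predicts a mean reduction of about 82% at 210 mg by Week 24. On one simulated set of 16 with negative changes, a normal log-link fit (not run in SAS) either stopped with an error or gave runaway coefficients from each of three starting points. The coverage figures above therefore describe a version of the model that can be fitted.

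**The case against.** The strongest objection is that the calculation does not describe the model in the SAP. With a log link on a mostly negative change, there may be no interval to under-cover. That stands. A reader might infer that the interval the SAP code prints will cover 82-87%. The documents do not support this, because the figures apply only once the link or response scale has been repaired and GENMOD kept. The point survives as a separate one, since repairing the link leaves the variance divisor and the quantile as they were.

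Second, the code is offered as a sample, and SAP section 7 defers detailed programming specifications to another document. An override could be placed there. But neither the SAP text nor its code specifies another variance estimator or quantile, so the plan as it stands does not fix a valid one. It is also true that the defaults are knowledge of the software, not something the SAP says.

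Third, the consequence is limited. The trial was stopped early, there is no p-value or decision rule, and the same endpoint is shown as observed values, absolute and percent change, with individual plots. A reader might infer a false efficacy claim or an invalid primary conclusion. Nothing in the documents supports that, and with a predicted reduction near 82% a wider interval may leave the qualitative message unchanged. This argues for lower severity; it does not make the label on the interval correct.

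**Conclusion.** The point holds, with moderate severity. If GENMOD is kept with its defaults after the link is repaired, the nominal 95% interval misses the true difference about 13% of the time at n=16 (100 - 86.8 = 13.2%), against 5% intended. The standard error is about 0.83 of its unbiased counterpart.

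The 87% figure assumes all 16 participants are analysed, all three fibrosis strata are occupied, and errors are normal with equal variances. Empty strata raise it to 88-90%. The 82% figure rests on an assumed 12 analysable participants and should not be read as what this trial will have. The formula is exact for a linear normal model and approximate for a log-link fit.

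**What to change.** Make the change together with the correction of link and response scale in SAP 3.4.1:

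- Replace PROC GENMOD by PROC GLM, or by PROC MIXED with REML and residual degrees of freedom, on the response scale adopted (for example log-transformed serum AAT). The variance then uses n-p and the limits use t(n-p). Neither procedure fits a log link, so the response scale has to be settled first.
- State this variance estimator and quantile in the SAP text as well as in the code.
- Report the analysed n and the residual degrees of freedom beside the estimate.
- If GENMOD must stay, use SCALE=PEARSON and also compute the limits with the t(n-p) quantile. SCALE=PEARSON alone is not enough.

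The cost is a few lines of SAP text and code, with no new data. The interval becomes about 1.35 times as wide at n=16 and 1.58 times at n=12, with five mean parameters.

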3.4.3 Secondary Endpoints

Analyses of Fibrosis, Steatosis, and Inflammation

Descriptive summaries will be provided for METAVIR scores, and Ishak scores. METAVIR scores are composed of a 2-letter and 2-number coding system that describes activity (A) and fibrosis (F). Ishak scores range from 0 (no fibrosis) to 6 (cirrhosis) and will be analyzed as a continuous variable.

Values and changes from baseline (if applicable) will be presented at each scheduled visit by treatment and overall. Listings of the individual parameters will be provided.

3.5 Pharmacokinetic (PK) Assessment

There is no PK analysis planned for the study.

3.6 Pharmacodynamic (PD) Assessment

There is no PD analysis planned for the study.

3.7 Safety Assessment

Safety and tolerability of study drug will be evaluated via the assessment of AEs, the change from Baseline in PFTs, 12-lead ECG, PE findings, vital signs, and clinical laboratory tests. All safety analyses will be performed on the Safety Population (unless specified otherwise) by actual treatment received and overall.

3.7.1 Adverse Events (AEs)

AEs will be captured from the date of informed consent through study completion. AEs will be defined as TEAEs if they have a start date on or after the administration of study drug during the treatment period, or if they occur prior to the administration of study drug and worsen in severity/grade or relationship to the investigation medical product after the administration of study intervention during the treatment period. Frequency and percentages will be used to summarize TEAEs, serious adverse events (SAEs), AEs of special interest (defined as injection site reactions), and TEAEs by relationship.

An overview of TEAEs will be provided including counts and percentages of participants with the following:

- Any TEAEs (overall and by maximum severity)
- Any TEAEs (overall and by relationship to study medication)
- Any TEAEs of special interest (overall and by injection site reaction grading)
- Any SAEs
- Any TEAEs leading to discontinuation of study drug
- Any AEs leading to death

Counts and percentages of participants will also be presented by system organ class and preferred term for each of the categories in the overview. Participants will be counted only once at each system organ class and preferred term level.

Listings will be presented specifically for TEAEs, SAEs, and TEAEs leading to discontinuation of study drug.

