Serum AAT & CRP m	Х			Х	Х		Х	Х	Х	Х	X		Х		Х	Х	Х	Х	X
Antidrug antibodies n	Х				Х			Х			Х		Х		Х				Х
Blood biomarkers of fibrosis °	Х				Х			Х			Х				Х		Х		Х
Blood biomarkers of inflammation	Х				Х			Х			X				Х		X		X
Samples for future analysis p	Х										X				Х				X

# Table 22: Treatment Period Schedule of Activities – Cohort 1

Dose #	1				2		3	4	5	6	EOT/ 7		8 a		9 a	10 a	11 a	12 a	13/ ET a1,b
Study day	1	2	3	15	29	30 °	57	85	113	141	169	211	253	295	337	421	505	589	673
Visit	V1	V2	V3	V4	V5	V6	V 7	V8	V9	V10	V11	P12 d	V13	P14 d	V15	V16	V17	V18	V19
Visit window (days)	_	_	_	±2	±2	_	±5	±5	±5	±5	±5	±5	±7	±5	±7	±7	±7	±7	±7
Plasma PK q	X	Х	Х	Х	X	Х	Х	Х	Х	Х	Х		Х		Х	Х	Х	Х	X
Vital signs r	Х	Х	Х	Х	Х	Х	Х	Х	Х	Х	X		Х		Х	Х	Х	Х	X
Physical examination	X	Xs	Xs	Xs	Xs	Xs	Х	Xs	Xs	Xs	Х		Xs		Xs	Xs	Xs	Xs	X
Weight	X										X				Х				X
12-lead ECG t	X	X		Х	X	X	Х	Х	Х	Х	X				Х		Х		X
CLDQ u	X							Х			X				Х				X
SGRQ u	Х							Х			Х				Х				X
FibroScan v											X				Х				X
MRE v											Х				Х				X
Liver biopsy											Х								X w
Record AEs	X	X	X	Х	X	X	Х	Х	Х	Х	X	X	Х	Х	Х	Х	Х	Х	X
Record SAEs x	Х	Х	Х	Х	Х	Х	Х	Х	Х	Х	Х	X	Х	Х	Х	Х	Х	Х	X
Concomitant medications/procedures	Х	Х	X	Х	Х	X	Х	Х	Х	Х	X	Х	Х	Х	Х	X	Х	Х	X
Attend visit fasting y	X										X				Х				X

Abbreviations: AAT: alpha-1 antitrypsin; AE: adverse event; AFP: alpha fetoprotein; BMI: body mass index; CLDQ: Chronic Liver Disease Questionnaire; COVID-19: corona virus disease 2019; CRP: C-reactive protein; DLCO: diffusion capacity of the lungs for carbon monoxide; DSMC: Data Safety Monitoring Committee; ECG: electrocardiogram; EOT: end of treatment; ET: early termination; FEV1: forced expiratory volume in one second; F/U: follow-up; I/E: Inclusion/Exclusion; FVC: forced vital capacity; MRE: magnetic resonance elastography; PK: pharmacokinetics; SAE: serious adverse event; SGRQ: St. George's Respiratory Questionnaire; UACR: urine albumin-creatinine ratio; UPCR: urine protein-creatinine ratio; WOCBP: women of childbearing potential.

- a Visits indicated are optional dosing visits that can be performed if the participant consents. If the participant does not want to continue with the optional dosing, they will receive their final dose at EOT/D169 and then continue into follow up.

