Record AEs	Х	Х	Х	Х	Х	Х	Х	Х	Х	Х	Х	Х	Х	Х	Х	Х	Х	Х	Х	Х	Х
Record SAEs w	Χ	Х	Х	Х	Х	Х	Х	Х	Х	X	Х	Х	Х	Х	Х	Х	Х	Х	Х	Х	Х
Concomitant medications/ procedures	Х	Х	Х	Х	Х	Х	Х	Х	Х	Х	Х	Х	Х	Х	Х	Х	Х	Х	Х	Х	X
Attend visit fasting x	Х										Х						Χ				Х

Abbreviations: AAT: alpha-1 antitrypsin; AE: adverse event; AFP: alpha fetoprotein; F/U: follow-up; CLDQ: Quality of Life Index for Patients with Chronic Liver Disease; CRP: C-reactive protein; DLCO: diffusion capacity of the lungs for carbon monoxide; DSMC: Data Safety Monitoring Committee; ECG: electrocardiogram; EOT: end of treatment; ET: early termination; I/E: Inclusion/Exclusion; MRE: magnetic resonance elastography; PE: physical examination; PK: pharmacokinetics; SAE: serious adverse event; SGRQ: St. George's Respiratory Questionnaire; UACR: urine albumin-creatinine ratio; UPCR: urine protein-creatinine ratio; WOCBP: women of childbearing potential; Z-AAT: the mutant AAT protein.

a Visit indicated are optional dosing visits that can be performed if the participant consents. If the participant does not want to continue with the optional dosing, they will receive their final dose at EOT/ D337 and then continue into follow up.

b Participants who terminate the stu y prematurely early termination "ET" will un ergo all activities as described under D673, with the exception of dosing.

- c Day 30 will always be the day after Day 29, regardless of when Day 29 occurs within the  $\pm$  2-day visit window.
- d The first dose of study intervention must be administered at the clinical site.
- e Post-bronchodilator values for DLCO and spirometry (FEV1 and FVC) will be recorded. The order of testing for recorded values should be 1) administer bronchodilator, 2) immediately perform DLCO, and 3) perform spirometry. On dosing days, DLCO and spirometry will be performed predose.
- f Collect and record the number and severity of pulmonary exacerbations since the last PFT assessment, resting peripheral oxygen saturation, smoking status including number of cigarettes per day, and use of AAT replacement therapy since the last visit. Assess and record the Modified Medical Research Council dyspnea scale.
- g For Dose 1 only, blood samples for hematology, clinical chemistry, and coagulation studies will be collected predose and at 6 hours (± 30 minutes) postdose. At other dosing visits, these samples will be collected predose only. See Section 10.2 for a detailed list of clinical laboratory parameters.

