# 2.1. Study Rationale

AATLD is a progressive condition resulting in liver fibrosis, and, in some patients, cirrhosis and even HCC. There is no effective treatment for patients with the toxic gain-of-function liver disease associated with AATD, other than standard supportive care, and, in those who progress to end-stage liver disease, organ transplantation. Given the substantial morbidity and mortality of AATLD and the burden of liver transplantation, there is a significant unmet need for a safe and efficacious treatment.

In nonclinical studies, belcesiran sodium (the drug substance for belcesiran) has been shown to significantly reduce target mRNA and AAT protein levels in transgenic mice expressing multiple copies of the human Z-mutant allele of *SERPINA1* and in cynomolgus monkeys expressing wild-type *SERPINA1* at doses of 0.1 mg/kg or greater. Additionally, in the transgenic mouse model of AATLD, belcesiran sodium significantly reduced hepatic globule levels, which is indicative of

reduced accumulation of aggregated human Z-AAT protein. Decreased cellular proliferation and hepatic fibrosis were also observed upon repeated administration of belcesiran sodium. These findings suggest that, by eliminating the toxic protein, belcesiran may prevent and reverse liver disease progression, eliminating the need for liver transplantation. These nonclinical pharmacology studies support the clinical evaluation of belcesiran to treat patients with AATLD.

DCR-A1AT-101 is an ongoing, Phase 1, single-ascending-dose (SAD) study of belcesiran in healthy volunteers. Participants in Study DCR-A1AT-101 received a single dose of DCR-A1AT (0.1, 1.0, 3.0, 6.0, or 12 mg/kg) or placebo and were followed for 56 days (treatment period) thereafter. At the end of the 56 day treatment period, any participant whose serum AAT protein concentration had not returned to  $\geq 80\%$  of baseline (or was not within the normal range) returned for PD monitoring visits (conditional follow-up) every 4 (±1) weeks for 2 months, then every 8 (±2) weeks for the next 4 months, and then every 12 (± 3) weeks for an additional 6 months or until AAT returned to  $\geq 80\%$  of baseline, whichever is shorter. Currently, all participants have completed the 56-day treatment period and follow-up continues for participants who met the criteria for conditional follow-up.

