Participants in Cohort 1 and 3 will receive monthly dosing for the first 24 weeks and then shift to quarterly dosing thereafter until week 96. Participants in Cohort 2 will receive monthly dosing for the first 48 weeks and then shift to quarterly dosing thereafter until week 96. Participants will continue the IMP throughout the study, unless the participant or investigator decide to discontinue IMP, or the participant withdraws from the trial or a discontinuation criterion is met.

All Participants in Cohorts 1 to 3 will have the option to undergo a liver biopsy at EOT/week 96. The biopsy at 96 weeks will inform about Z-AAT levels and provide further information about possible improvements in liver histology. Biopsy findings will be correlated with changes in non-invasive markers of liver disease and liver stiffness.

After the EOT visit, all participants will be followed up for 48 weeks. In addition, Cohorts 1 and 2 will be followed for an additional 48 weeks to inform about the duration of potential treatment

effects. If a participant in Cohorts 1 or 2 does not wish to extend the treatment period to 96 weeks, follow-up will stop after the 48-week follow-up period.

There are 3 interim analyses planned for this trial. Interim analyses for Cohorts 1 and 2 will take place after all participants in Cohorts 1 and 2 complete 24 weeks and 48 weeks of treatment, respectively. The third interim analysis will be performed when all the participants in Cohort 3 have completed 24 weeks of treatment. The third interim analysis will evaluate the dose-response relationship on efficacy and safety assessments of the two doses of belcesiran. If based on the interim analysis it is concluded that one dose is more favorable with respect to effect while showing no overall difference in safety – the least favorable dose-arm can be stopped.

The trial will be monitored by an independent external DSMC. The DSMC will review accumulating data from the trial in an unblinded fashion to ensure adequate monitoring of safety. The timing and scope of the review meetings will be defined in the DSMC charter.

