# 9.3. Statistical Analyses

#### 9.3.1. Analyses of Primary Endpoints

#### 9.3.1.1. Safety Analysis

All safety analyses will be performed on the Safety Population. Adverse events will be defined as TEAEs if they have a start date on or after the administration of study drug during the treatment period, or if they occur prior to the administration of study drug and worsen in severity/grade or relationship to the study intervention after the administration of study intervention during the treatment period. Frequency and percentages will be used to summarize TEAEs, SAEs, and AEs of special interest by relationship. Laboratory values will be reported by grade and summarized, if applicable.

Change from baseline and observed values will be summarized where applicable. Laboratory analytes will be presented by a shift from baseline and graphically represented in mean values over time where applicable. Vital signs, ECG, and PFTs (i.e., FEV1, FVC, FEV1/FVC, and DLCO) will be summarized as continuous parameters.

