3.1.6 Handling of Dropouts and Missing Data Values

As statistical analyses will be descriptive in nature, no missing data will be imputed unless otherwise specified. For the classification of treatment emergent adverse events (TEAE) and concomitant medications, the following imputation rules will be applied:

Dates will be printed in ISO 8601 date format (YYYY-MM-DD). If only year and month are available, date will be displayed as YYYY-MM. If only year, then just YYYY. Dates that are missing because they are not applicable for the subjects will be output as "NA", unless otherwise specified.

Treatment emergent adverse events and concomitant medications with missing start dates will be considered as treatment-emergent unless the partial date excludes that possibility. Otherwise, the first day of the month will be used to impute the missing start day and January will be used to impute missing start month.

The purpose of imputing day and month values is to determine treatment emergence or whether a medication is a prior or a concomitant medication. The imputed value will not be presented in the listings. Only the derived TEAE status and concomitant medication status will be presented.

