3.3 Subject Data and Study Conduct

3.3.1 *Participant Disposition*

Counts and percentages of participants who completed the treatment period, who completed the treatment period but did not complete the follow-up, who completed the study, and who discontinued from the study will be summarized based on the Enrolled Population. Reasons for early discontinuation will also be summarized.

3.3.2 *Demographic and Baseline Characteristics*

The following demographic and baseline characteristics will be summarized:

- Age (years)
- Sex
- Race
- Ethnicity
- Height (cm)
- Weight (kg)
- Body mass index (BMI) (kg/m²)
- F1, F2, F3 and F4

- AST
- ALT
- Serum AAT
- Receiving augmentation therapy

Demographic and baseline characteristics will be summarized with descriptive statistics or counts and percentages of participants as appropriate by treatment and overall, based on the Safety Population.

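### Does the lack of a stated end to the treatment period undermine the treatment-emergent adverse event tables?

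*SAP*

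**What the plan says.** SAP 3.7.1 gives the rule for new-onset events: "AEs will be defined as TEAEs if they have a start date on or after the administration of study drug during the treatment period". Events present before dosing count if they worsen after dosing, with the same limit to the treatment period. Protocol 9.3.1.1 uses the same condition: "start date on or after the administration of study drug during the treatment period". Neither section adds a number of days after the last dose.

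The documents do show where treatment is planned to end. In the treatment schedules of protocol section 1.3, footnote a covers participants who decline optional dosing: in Cohort 1 "they will receive their final dose at EOT/D169 and then continue into follow up", and in Cohort 2 "they will receive their final dose at EOT/ D337 and then continue into follow up". Those who accept it have their last dose on Day 673, the final column of both treatment-period schedules. Protocol 4.1 continues: "After the EOT visit, all participants will be followed up for 48 weeks". The disposition summary in SAP 3.3.1 also separates the periods, with a category for participants "who completed the treatment period but did not complete the follow-up".

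For incomplete dates, SAP 3.1.6 states: "Treatment emergent adverse events and concomitant medications with missing start dates will be considered as treatment-emergent unless the partial date excludes that possibility".

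**The concern.** The incidence and nature of TEAEs is a primary endpoint for Cohorts 1 and 2, the only cohorts to be analysed. Adverse events are collected throughout follow-up, and SAP 5.2 locks the database only after follow-up, so events that start after the last dose will be in the data and must be classified.

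The defining sentence has two readings. On reading A the onset must fall inside the treatment period, so a non-serious event that begins in follow-up is left out of the TEAE overview and its system organ class and preferred term tables. On reading B the limit attaches to the giving of drug, so every event after the first dose counts.

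The pharmacology makes the question a fair one. Protocol 2.2.4 reports that mean serum AAT in healthy volunteers was still about 48% (1.0 mg/kg) to 78% (12.0 mg/kg) below baseline at Day 57 after a single dose, and protocol 2.3.3 equates 210 mg to about 3 mg/kg. A cut-off at the last dose could then leave out events that begin while the drug is still acting. The sponsor also stopped the trial early, so some participants may not have an end of treatment on the planned day.

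**Working it through.** The plan gives no figure to reproduce. The check measures how far the two readings differ, then asks what each would change.

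**Planned time after the last dose** (days from the dose-regimen figure in protocol 1.2 and the visit windows in SAP 3.1.2; follow-up length from protocol 4.1). Difference = last follow-up day − last dose day; share = difference ÷ last follow-up day.

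- Cohort 1, no optional dosing: 505 − 169 = 336 days; 336/505 = 66.5%.
- Cohort 2, no optional dosing: 673 − 337 = 336 days; 336/673 = 49.9%.
- Either cohort with optional dosing, 48-week follow-up: 1009 − 673 = 336 days; 336/1009 = 33.3%.
- Either cohort with optional dosing, 96-week follow-up: 1345 − 673 = 672 days; 672/1345 = 50.0%.

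These are planned durations in a trial that was stopped early. They show the distance between the readings and say nothing about how many events fall there.

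**Optional period.** The dose-regimen figure labels it separately. If it were not counted as treatment, a further 673 − 169 = 504 days (Cohort 1) or 673 − 337 = 336 days (Cohort 2) would be in doubt. Participants are still being dosed then, and the schedules headed as treatment-period schedules run to Day 673 in both cohorts. An analyst has no good reason to exclude it.

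**Early stoppers.** Protocol 7.1.1 asks those who discontinue drug to keep their scheduled visits, and protocol 7.2 provides an early termination visit for those who leave the study. Reading A therefore does not always mean zero days after the last dose. That holds only when the last dose is given at the end-of-treatment visit.

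**Partial dates.** Suppose an onset is known only to be in the month of the last dose, and the first dose was in an earlier month. Onset on treatment is possible, so SAP 3.1.6 does not exclude it, and imputing the first of the month puts it on or before the last dose. It is treatment-emergent on both readings. For a later month, a complete date raises the same question. The rule adds no separate problem, and its default is inclusive.

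**What the readings leave unchanged.** The overview in SAP 3.7.1 counts serious events and events leading to death without the treatment-emergent condition. SAP 7 puts all available data in participant listings. SAP 3.1.5 rules out hypothesis tests.

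**Scale.** With full enrolment at 3:1, each cohort has 6 active and 2 placebo participants, or 12 and 4 combined. Moving one participant into or out of a row changes the combined percentage by 1/12 = 8.3 points (active) or 1/4 = 25 points (placebo). Percentages this coarse have to be read with the listings, whichever rule is used.

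**The case for a change.** The best case for a change is that a primary-endpoint definition belongs in the SAP, that listings give no incidence by arm, and that one sentence and one derived flag would settle it at little cost. The ambiguity is real, and no text sets the end of the period for participants whom the sponsor stopped. Those points stand.

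Other parts are weaker. It would be too strong to say that the documents never show when treatment ends, because the schedules and the follow-up text place it at the end-of-treatment visit. The wider wording in protocol 8.3.1, for pre-existing conditions that worsen after the first dose, tells sites what to record; the analysis wording agrees across protocol and SAP. The description of the Phase 1 study, whose participants "were followed for 56 days (treatment period) thereafter", shows that a treatment period can include observation after dosing, but it belongs to another protocol and does not settle the grammar here. Persistent AAT reduction is pharmacodynamic evidence from healthy volunteers. Protocol 2.2.4 also reports no serious or severe events in that study, so it does not demonstrate delayed harm.

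A window would also have to be chosen. One dosing interval is 29 − 1 = 28 days (monthly) or 421 − 337 = 84 days (quarterly). The first is half of the 56 days (57 − 1) over which the effect was seen to persist, and the pair would give participants on the same drug different windows. The documents support neither figure as a TEAE window, and reasonable statisticians would differ.

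**Conclusion.** No change to the plan is called for. A detail has not been written down, and the analysts can fill it sensibly from the schedules. The gap bears only on how non-serious events starting after the last dose are tabulated: up to 336 planned days per participant, or 672 after extended treatment with the longer follow-up. The excluding reading is an inference, and the other reading of the same sentence already counts every event after the first dose. Serious events, deaths and the all-data listings are the same either way.

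This rests on three assumptions: that the flag is derived in the same way for both arms and for completers and early stoppers alike; that the separate programming specifications announced in SAP 7 record the end date used; and that the listings are produced as planned. The conclusion would be different in a trial that tested TEAE rates between arms or kept no record of later events. Neither applies to this descriptive report on at most 16 participants.
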